3.9 Data analysis

To explore the difference between game performance in PwMCI and healthy comparison group (RQ1), the Unpaired t-test or Mann-Whitney U test as appropriate (155), with an α level of 0.05, will be applied. If the mean difference is statistically significant, it indicates that G3 can classified older adults with typical cognition and older adults with MCI based on their game performance. In addition, a two-way factorial multiple analysis of covariance (MANCOVA) (155) will be performed to compare the effects of demographics as covariates on the differences between groups.

To explore the association between the game performance and traditional cognitive tests, including MoCA and Qmci (RQ2), correlational analysis (155) between the game metrics and the scores of each traditional cognitive tests, including total score sub-scores such as memory and executive functions will be conducted. If the correlation coefficient (r) is positive closer to one, it means that the concurrent validity of G3 as an MCI screening tool is good.

To investigate the diagnostic accuracy of the game-based screening (RQ3), formulas will be used as follows:

Sensitivity: Proportion of true positives correctly identified = $\frac{TP}{TP+FN}$

Specificity: Proportion of true negatives correctly identified = $\frac{TN}{TN+FP}$

Accuracy: Overall correctness of the testx = $\frac{\text{TP+TN}}{\text{Total Population}}$

Where TP: True Positives, TN: True Negatives, FN: False Negatives, FP: False Positives (155). Additionally, the interpretation of the Receiver Operating Characteristic (ROC) and Area Under the Curve (AUC) will be used for examination of diagnostic accuracy (155). The ROC curve is a graphical plot that illustrates the diagnostic ability of a binary classifier system as its discrimination threshold is varied. The curve is created by plotting the True Positive Rate (TPR) against the False Positive Rate (FPR) at various threshold settings (155).

The following steps will be used to calculate the ROC curve:

Firstly, the True Positive Rate (TPR), also known as sensitivity or recall, will be determined using the formula:

$$TPR = \frac{TP}{TP + FN}$$

Secondly, the False Positive Rate (FPR), also known as (1 - specificity), will be determined using the formula:

$$FPR = \frac{FP}{FP+TN}$$

Finally, the ROC curve will be calculated and plotted. TPR and FPR need to be calculated for various threshold values. Then, TPR (y-axis) against FPR (x-axis) for each threshold will be plotted. The closer the ROC curve is to the upper left corner, the higher the test's accuracy, as this position represents a sensitivity of 1 and a false positive rate of 0 (specificity of 1). An ideal ROC curve has an AUC of 1.0. An AUC of 0.5 indicates no discrimination, 0.7 to 0.8 is acceptable, 0.8 to 0.9 is excellent, and above 0.9 is considered outstanding (155,156).

To investigate if the game performance is an associated factor with cognitive status controlled by demographic variables (RQ4), logistic regression analysis (157) will be used. For all variables, categories will be combined into broader categories, when possible, to improve the power of the logistic regression model (158). Chi-Square test will be used to determine if there is a significant

association between variables and cognitive status. Principal Component Analysis (PCA) will be used to reduce the number of variables in a dataset while preserving as much variability (information) as possible (159). To determines which factors to retain based on explained variance, and Eigenvalue Cut-Off of 1 will be applied. Following this, logistic regression model will be run with the included variables. The performance of the logistic regression model with be evaluated using ROC analysis and test characteristics (160).

To compare the differences between the level of anxiety while playing the game and while traditional cognitive tests in older adults with typical cognition and with MCI (RQ5), either the Paired t-test or Wilcoxon Signed-Ranks test (155) will be used as appropriate, with an α level of 0.05, to compare the anxiety level in the two conditions- while playing the games and while performing MoCA. If the mean difference is significant and lower while playing the game compared with MoCA and Qmci, it means that the G3 causes less anxiety compared to the traditional cognitive screening tools.

To explore the usability of the game-based screening (RQ6), the SUS results will be calculated and interpreted as follows:

To calculate the SUS score, the following steps will be carried out: first sum the score contributions from each item. Each item's score contribution will range from 0 to 4. For items 1,3,5,7, and 9 the score contribution is the scale position minus 1. For items 2,4,6,8 and 10, the contribution is 5 minus the scale position. Second, multiply the sum of the scores by 2.5 to obtain the overall value of SU. SUS scores have a range of 0 to 100 (152). A SUS score of 85 or higher indicates exceptional usability, while a score below 70 is considered unacceptable (161).

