The MoCA is one of the most common paper-based cognitive tests that evaluate short-term memory, visuospatial skills, executive function, attention, concentration, working memory, language, and orientation within 10-15 minutes (16). The MoCA demonstrates high test-retest reliability, good internal consistency, as well as strong concurrent and construct validity (109). Content validity is also supported by a high correlation between MoCA and MMSE scores (16). Sensitivity and specificity vary depending on the cut-off points used, with reported sensitivity ranging from 67% to 100% and specificity from 50% to 95% (108). Research also suggested 89% sensitivity and 79% specificity for MCI detection, with the cutoff point of 26 for MCI and 18 for dementia (110). The AUC for MoCA is 0.84 in differentiating MCI from controls. The MoCA is also adjusted for educational level (16). Despite its advantages, the MoCA has some limitations including educational bias for low level of education, associated cost for usage, and the requirement for administrator training (108).

The SLUMS is a cognitive screening tool that can be administered in less than 10 min to assess attention, immediate recall, orientation, delayed recall, calculation, visuospatial abilities, and executive functions (18). However, the SLUMS is less accurate for MCI detection compared to the MoCA, with sensitivity ranging from 73% to 95% and specificity ranging from 65% to 81%, with education adjustment (111). Regarding psychometric properties, although the existing literature offers initial support for the SLUMS, further research is necessary to assess its reliability, validity, and application across more diverse populations (111).

The Qmci is a brief paper-based cognitive test designed to differentiate between normal cognitive function, subjective cognitive disorders, MCI, and early dementia. It assesses

orientation, memory, language, visuospatial skills, and executive function in 3-5 minutes. The Qmci demonstrates good test-retest reliability and validity (112–114). With a cut-off point <62, for MCI detection, it achieves a sensitivity of 90% and specificity of 87%, and the AUC for differentiating MCI form controls is 91% (115). Compared to the MoCA, the Qmci's primary advantage is its brevity, requiring only half the time to complete while offering greater accuracy for MCI detection (115,116). Additionally, the Qmci provides different cut-off points according to both age and educational level (117).

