3.6 Variables

The study variables are the following:

- Game performance collected through various game metrics, including total time of
 playing, the ability to complete the whole game, the ability to manage the budget, number
 of errors, the number of checking the shopping list, and the game performance accuracy.
 - Total Time of playing: This numerical variable refers to the total time that takes to complete all 6 stages in seconds with the maximum of 1800 seconds.
 - The ability to complete the game: This binary variable (1= Could complete, 0= Could not complete) refers to the participant's ability to complete all the 6 stages of the game.
 - The ability to manage the budget: This binary variable (1 = Could manage, 0 =
 Could not manage) refers to the participant's ability to keep their purchases equal to or below the budget limit provided for each level.
 - The number of errors: This numerical variable refers to the total number of mistakes made by participants, including mistaken, missed, and repeated items purchased.
 - The number of times the participant opens up the reading list: This numerical variable refers to the total number of times the participant open and check the shopping list within the 6 stages.
 - O The game accuracy: This numerical variable represents the success in the game, ranging from 0 to 100, where higher values mean higher game performance.

Demographics

 Age (In number of years): It refers to the chronological age of an individual in years at the time of data collection. This variable is considered as numerical in this study.

- Sex at birth: It refers to sex assigned at birth. Categories for this variable are male and female.
- Level of education: It refers to the highest degree or level of school completed by the participants. Categories for this variable are elementary school, high school, bachelor's degree, master's degree, and higher.
- Technology savvy: This categorical refers to the familiarity and experience of the
 participants with technology. It will be collected and measured based on the
 number of technological devices they use and the frequency of their usage.
- Living status: It refers to the participants' living condition. Categories for this
 variable are living alone, living with family, and living in an institution

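### Section 3.9 reads a significant group difference at 0.05 as proof that G3 can classify MCI, but game performance is six metrics and none is named as the one that counts

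*Protocol*

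**What the plan says.** Protocol section 3.6 introduces the variable as "Game performance collected through various game metrics" and lists six: total playing time, completing the game, managing the budget, number of errors, number of times the shopping list is opened, and game accuracy (0 to 100, higher is better). Completion and budget are binary and the other four numerical. No composite is defined and no metric is singled out.

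Section 3.9 plans for RQ1 that "the Unpaired t-test or Mann-Whitney U test as appropriate (155), with an α level of 0.05, will be applied". The inference is fixed in the next sentence: "If the mean difference is statistically significant, it indicates that G3 can classified older adults with typical cognition and older adults with MCI". A MANCOVA follows, to examine demographic covariates. It is not described as a step that must be passed before single metrics are interpreted.

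For RQ2, section 3.9 correlates the game metrics with MoCA and Qmci scores, "including total score sub-scores such as memory and executive functions will be conducted". No alpha is given there. The criterion is the size of the coefficient: "If the correlation coefficient (r) is positive closer to one, it means that the concurrent validity of G3".

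Section 3.3 sets 58 participants, 29 per group, and names diagnostic accuracy and validity testing as the primary objectives.

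**The concern.** The RQ1 rule speaks of one mean difference, but the protocol defines six quantities that could show one. Nothing says whether one named metric, any metric or all metrics must be significant. The natural reading of a question asking whether there is any difference is that one significant metric will do. On that reading the 5% applies to each test and not to the statement made about the game.

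At stake is the claim that the game separates people with MCI from people without it. A first study of an untested tool will be used to decide whether a larger one is worthwhile. Choosing the metric after the results are seen would not cure the problem.

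RQ2 has the same gap in milder form. Every metric meets two totals and an open list of sub-scores, and no pairing is identified as the one that answers whether the game is concurrently valid.

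**Working it through.** **Inputs.** Alpha 0.05 (3.9; sidedness not stated, taken as two-sided). Six metrics, four of them numerical (3.6). 29 per group, 58 in total (3.3). The correlation between metrics is not given, so a range from 0 to 0.9 is shown.

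**The plan's own figure.** With one test, the chance of a false positive is 1 − 0.95¹ = 5%. The stated alpha therefore describes the RQ1 conclusion only if a single metric decides it.

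**RQ1, any of several metrics suffices.** For k independent tests with no true difference, P(at least one p < 0.05) = 1 − 0.95^k.

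- k = 6: 1 − 0.95⁶ = 1 − 0.735 = 26.5%.
- k = 4: 1 − 0.95⁴ = 1 − 0.815 = 18.5%.

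For correlated metrics, t-tests were simulated under no difference, 29 against 29, with equal correlation between metrics:

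| Inter-metric correlation | Six metrics | Four numerical metrics |
|---|---|---|
| 0 | about 26–27% | about 18% |
| 0.3 | about 24% | about 17% |
| 0.5 | about 21% | about 16% |
| 0.7 | about 17% | about 13% |
| 0.9 | about 11% | about 9% |

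The simulation treats all metrics as continuous. Two of the six are binary, so the six-metric column is approximate; the four-metric column avoids that difficulty. In every row the rate exceeds 5%, by roughly two to five times.

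**Power under the remedies.** Assume a standardised difference of 0.7 (the effect size in 3.3, read here as a mean difference), 29 per group and a two-sided t-test. One named metric at 0.05 has about 75% power. Bonferroni over six (0.05/6 = 0.0083 per test) leaves about 48% for each metric.

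**RQ2.** Section 2.2.5 says the MoCA serves to "evaluate short-term memory, visuospatial skills, executive function, attention, concentration, working memory, language, and orientation", which is eight domains, and lists five for the Qmci. If each domain were one scored sub-score, there would be 6 × (2 + 8 + 5) = 90 correlations. That is an assumption, since 2.2.5 describes what the tests assess and not how they are scored.

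- At n = 58, nominal p < 0.05 needs |r| of about 0.26, and 90 × 0.05 = 4.5 null correlations would pass it on average.
- Under the protocol's own criterion, the size of r, the largest of 90 independent null |r| averages about 0.35. The chance that any reaches 0.5 is 1 − (1 − 0.0000643)⁹⁰ = 0.6%, and for 0.7 it is about 1 in 10 million.
- If the correlations were run within one group of 29, the chance that any reaches 0.5 is 1 − (1 − 0.00575)⁹⁰, about 40%, and for 0.7 about 0.2% (independence assumed). Section 3.9 does not specify a by-group analysis, though the wording of RQ2 in 1.3 allows one.

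**The case against.** The protocol calls this a feasibility study and introduces RQ1 and RQ2 as exploration. Diagnostic accuracy, a primary objective, is judged by sensitivity, specificity and AUC, not by the RQ1 p-value. Multiplicity procedures are commonly left to an analysis plan, which is not at hand. Section 3.9 never says in words that each metric is tested separately.

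Most of this stands, and it limits the point. The absence of an adjustment procedure is not itself the fault. What remains is that 3.9 writes down a decision rule, in confirmatory terms, on a quantity the document leaves as six. An unseen plan could mend that, but the rule as written does not say what it tests.

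A reader might infer more: that chance will usually produce positive findings, and that noise among some 90 correlations will pass as validity. The document does not support this. For RQ1 the figure is at most about 27%. For RQ2 the high chance of at least one nominal p < 0.05 (99% for 90 independent correlations, 29% at a within-set correlation of 0.9) describes a rule that 3.9 does not use. It asks for r near one, which chance will not produce at n = 58.

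**Conclusion.** The point holds for RQ1. As written, a significant difference on an unnamed one of six metrics would be read as ability to classify, with a false positive rate of about 11% to 27% (about 9% to 18% if only the four numerical metrics are tested) in place of 5%. This assumes that significance on any one metric is enough, that tests are two-sided, and that the inter-metric correlation lies between 0 and 0.9. The MANCOVA does not protect against it, because nothing is made conditional on its result.

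For RQ2 the conclusion is weaker. There are many comparisons and no lead pairing, but the criterion is the size of r, so this is a matter of labelling and not an inflated error rate. Formal control of the remaining comparisons, by Holm or a false discovery rate, is a matter of preference in a feasibility study and is not needed.

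**What to change.** In section 3.9:

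- **RQ1.** Name one metric, before any data are analysed, on which the conclusion rests at 0.05. Game accuracy is a reasonable example: it runs from 0 to 100 and higher is better. Section 3.6 should then state how it is calculated. Report the other five metrics as supportive, with no claim about classification from them alone.
- **RQ2.** Make that same metric against the MoCA total and the Qmci total the test of concurrent validity, and label the sub-score correlations exploratory. Game accuracy also suits the rule asking for a positive r; for time and errors, where higher is worse, a valid game would give a negative one.

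The cost is a few sentences, with no added participants or procedures. RQ1 keeps about 75% power under the assumption above. The downside is that a difference seen only on a non-lead metric could not support the RQ1 conclusion and would have to be carried forward as a hypothesis for the larger study.

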1.3 Research questions

The present study aims to respond the following research questions (RQ).

- 1. Is there any difference between the game performance of older adults with typical cognition and individuals with MCI?
- 2. What is the concurrent validity of the game-based screening for MCI detection?
 - 2.1 Is there any relationship between game performance and total score of traditional cognitive tests (MoCA score and Quick MCI (Qmci)) in older adults with typical cognitive and older adults with MCI?
 - 2.2 Is there any relationship between the sub-MoCA scores and sub-Qmci scores and the game metrics in older adults with typical cognitive and older adults with MCI?

- 3. What is the diagnostic accuracy of the game-based screening assessed by sensitivity, specificity, accuracy, and the Area Under Curve (AUC) of the game-based screening for MCI detection?
- 4. Is game performance an associated factor with cognitive status controlled by demographic variables?
- 5. Is there any difference between the level of state anxiety while playing the G3 game and while administering traditional cognitive tests in older adults with typical cognition and individuals with MCI?
- 6. What is the usability of the G3 as a game-based screening?

2. Literature review

This chapter will address several key areas essential for understanding the use of SCGs in cognitive screening for MCI. It will begin with an overview of cognitive functions and their domains, followed by a discussion of MCI, its prevalence, and associated brain changes. The review will then examine cognitive changes with aging and MCI, traditional cognitive tests used for MCI diagnosis, and their limitations. It will explore digital technologies for MCI screening, focusing on the potential of SCGs. Finally, the chapter will highlight research gaps and propose directions future studies, emphasizing the investigation of the G3, a SCG designed for older adults, for MCI detection.

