to examining the relationship between game performance and cognitive status, requiring a moderate number of participants. Thus, this study, designed with a statistical power of 0.8, an alpha level of 0.05, and a medium effect size of 0.7, requires a minimum sample size of 58 participants. Twenty-nine older adults (65 and above) who meet the diagnostic criteria for MCI, and 29 older adults with typical cognition will be eligible to participate in the study. Other reasons for justifying the sample size include: 1) The statistical analyses to answer questions that aim to compare two conditions, or two groups requires a smaller sample size; and this small sample size is insufficient to justify correlational analysis. 2) the "Events Per Variable" (EPV) rule is often used in statistical modeling, particularly in logistic regression, to determine the minimum sample size needed to ensure reliable and valid results. The general rule is to have at least 10 events (outcomes of interest) for each predictor variable (151). Therefore, using regression analysis to explore the six associated factors (game performance, age, sex, educational level, tech savviness, and living status) with the presence of MCI would necessitate 60 events (instances of the outcome of interest). Assuming an equal distribution of events and non-events, at least 120 participants would be needed in total to achieve 60 events, ensuring that each predictor variable is adequately supported by the data and enhancing the reliability of the statistical model. However, for a feasibility study involving a brand-new, untested test, it is not ethical to recruit a large sample size and burden vulnerable older adults with participation. Besides, at this point of the study, it is not known how many independent variables will be included in the model and that depends on the results of the factorial analysis that precedes the logistic model. Therefore, I aim to treat the research about the associated factors with the presence of MCI (RQ4) as a pilot to gather preliminary data. This approach can help refine the research design and hypotheses, and the results can be used to justify the need for a larger study

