in the future. Additionally, based on the data, a simpler model with only the strongest predictors will be used to produce a more reliable regression model. Thus, for an initial study on a new test, correlational analysis is the most practical choice, allowing us to assess concurrent validity without requiring an excessively large sample size.

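### RQ1 reads a significant group difference as proof that G3 can classify, which can contradict the plan's own AUC scale; RQ4's data-driven model rule does not secure the demographic control it asks for

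*Protocol*

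**What the plan says.** **RQ1.** Protocol 3.9 compares game performance between the groups by "the Unpaired t-test or Mann-Whitney U test as appropriate", at α = 0.05, and then gives the reading: "If the mean difference is statistically significant, it indicates that G3 can classified older adults with typical cognition and older adults with MCI". A MANCOVA with demographics as covariates is added.

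**RQ3.** The same section assesses diagnostic accuracy separately, by sensitivity, specificity, accuracy and ROC analysis. It grades the AUC: 0.5 is no discrimination, "0.7 to 0.8 is acceptable, 0.8 to 0.9 is excellent", and above 0.9 is outstanding.

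**RQ4.** Protocol 1.3 asks: "Is game performance an associated factor with cognitive status controlled by demographic variables". Section 3.9 repeats that aim, runs chi-square tests and a PCA with an eigenvalue cut-off of 1, and then says the "logistic regression model will be run with the included variables".

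Section 3.3 counts six candidate factors: game performance, age, sex, education, technology savviness and living status. It adds that "it is not known how many independent variables will be included in the model and that depends on the results of the factorial analysis" and that "based on the data, a simpler model with only the strongest predictors will be used to produce a more reliable regression model". It treats RQ4 as a pilot whose results may justify a larger study.

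**The concern.** **RQ1.** A test of means asks whether two distributions are centred differently. Classification depends on how far they overlap. With 29 per group, a difference can be significant while the overlap is still large. Section 3.3 names diagnostic accuracy and validity as the primary objectives, so a sentence that turns p < 0.05 into ability to classify bears on the study's main conclusion. A report that follows the text could say under RQ1 that G3 classifies and under RQ3 that the same metric falls short of acceptable.

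**RQ4 (lesser).** Control by demographics means that the demographics are in the model. A rule that keeps only the strongest predictors can remove them, and can remove game performance too. The reported association would then not be the one asked for. Age and education matter most here: section 2.2.1 links both to MCI, and section 2.3.5 reports correlations of both with completion time in another shopping game.

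**Working it through.** **Inputs.** 29 per group (3.3), α = 0.05 and the two tests (3.9, RQ1), and the AUC scale (3.9, RQ3). The protocol does not state sidedness, so two-sided is assumed. The calculation takes 29 per group as given and does not depend on how the total of 58 was derived.

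**Step 1. AUC at the edge of significance, t-test.**
- Critical t with 56 df = 2.003.
- Critical standardised difference: d = 2.003 × √(2/29) = 2.003 × 0.2626 = 0.526.
- Under equal-variance normality, AUC = Φ(d/√2) = Φ(0.372) = 0.645.
- At the midpoint cut-off, sensitivity = specificity = Φ(d/2) = Φ(0.263) = 0.604.

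**Step 2. The same edge, Mann-Whitney.** U divided by 29 × 29 = 841 is the empirical AUC, so no normality assumption is needed. From the exact null distribution without ties, the smallest significant U is 547: AUC = 547/841 = 0.650, p = 0.0495.

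**Step 3. p-value that matches an AUC of 0.70.**
- t-test: d = √2 × Φ⁻¹(0.70) = 0.742; t = 0.742/0.2626 = 2.82; p = 0.0066.
- Mann-Whitney: U = 589, AUC = 589/841 = 0.700, p = 0.0083.

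| Observed AUC | p, t-test | p, Mann-Whitney | RQ1 sentence | RQ3 scale |
|---|---|---|---|---|
| about 0.65 | 0.05 (at 0.645) | 0.0495 (at 0.650) | can classify | below acceptable |
| 0.70 | 0.0066 | 0.0083 | can classify | lower edge of acceptable |

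Any p between about 0.008 and 0.05 therefore gives the two readings in conflict.

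**Step 4. How often, for one continuous normal metric (noncentral t).** If the true AUC is 0.60, RQ1 is significant in 27% of studies, and 19% of studies are significant with an observed d under 0.742. If the true AUC is 0.65, the figures are 53% and 29%.

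**Step 5. Precision of the RQ3 AUC (Hanley-McNeil, 29 per group).** At AUC 0.70 the variance is [0.21 + 28 × (0.5385 − 0.49) + 28 × (0.5765 − 0.49)]/841 = 0.00474, so SE = 0.069 and the 95% CI is 0.57 to 0.83. At 0.645 the SE is 0.073 and the CI is 0.50 to 0.79.

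**Step 6. RQ4.** The plan's events-per-variable figure reproduces: 6 × 10 = 60 events, and 60/0.5 = 120 participants. With 29 events, six predictors have 29/6 = 4.8 each, three have 29/3 = 9.7, and four have 29/4 = 7.3. Simplifying is thus reasonable. Set side by side, though, 1.3 and 3.9 require demographic control, while 3.3 lets the data choose the terms and reserves a place for none.

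How often age would drop out depends on a rule that the document does not give. With an assumed age gap of 0.3 to 0.5 SD, keeping the best three of six by |t| drops age in 44% to 26% of simulated studies. Keeping age only if p < 0.05 drops it in 81% to 52%. The spread shows that no single rate can be stated.

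**The case against.** **RQ1.** The fair reply is that RQ1 asks only about a difference, the planned test answers that, and RQ3 judges classification with suitable measures. A careful report would show both. This is true and limits the harm, but nothing in 3.9 withdraws the RQ1 sentence or gives RQ3 precedence. It also stands that section 3.6 lists six game metrics, two binary and two counts, with playing time capped at 1800 seconds. The no-ties and normal-model figures describe a continuous metric, and the rates in step 4 assume that the same metric is used in RQ1 and RQ3.

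**RQ4.** Much of the defence stands. RQ4 is declared a pilot, and 3.11 admits that the sample is small for a reliable regression. The PCA need not remove demographics: the text does not say which variables enter it, and if they all do, demographics remain as loadings. The RQ1 MANCOVA already plans a related demographic-adjusted comparison, although it does not give RQ4's adjusted association.

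**Stronger readings that a reader might infer.**
- *That demographics will drop out at some known rate.* The document gives neither a selection rule nor group gaps; the rates above are illustrations.
- *That selection inflates false positives for the game effect.* Simulation with no true game effect, and age kept only if p < 0.05, gave 3% to 5% overall, against about 4% with age always kept. Inflation appeared when age was always left out (up to 14%), and no section specifies a game-only model.
- *That the ROC evaluation of the RQ4 model is a further error.* The model is built and evaluated on the one sample described, so its AUC is an apparent value, but the protocol does not claim otherwise.

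**Conclusion.** The RQ1 sentence is wrong as written. At 29 per group, just reaching p = 0.05 corresponds to an AUC of about 0.645 to 0.650 and, under the normal model, to sensitivity and specificity of about 0.60. That is below the protocol's own 0.7. The result rests on a two-sided test of a continuous metric, with equal-variance normality for the t-test figure and no ties for the Mann-Whitney figure.

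The RQ4 point is real but smaller. The text asks for demographic control and then adopts a rule that does not secure it, nor a place for game performance. The fault is that the stated question may go unanswered. Neither a drop-out rate nor a bias in the game effect has been established.

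**What to change.** **RQ1 (3.9).** Replace the sentence with: *A significant difference indicates that game performance differs between the groups; classification is judged in RQ3 only.* Report the RQ3 AUC, sensitivity and specificity with 95% confidence intervals, and read the AUC against the bands already given. The cost is a less favourable conclusion and wide intervals: 0.57 to 0.83 at an AUC of 0.70, and 0.51 to 0.83 (Wilson) for a sensitivity of 20/29.

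**RQ4 (3.3).** State that the model always keeps game performance and a small prespecified set of demographics, whatever their significance. Age and education are one reasonable choice, given sections 2.2.1 and 2.3.5. Education would be collapsed to one term, which 3.9 allows, and the other demographics would go into labelled sensitivity models. The cost is 9.7 events per variable, slightly under the plan's 10 (7.3 with one more term), and fewer demographics adjusted for jointly. Sex would be among those left to sensitivity models although 2.2.1 links it to MCI, so the choice of set is open to debate.

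**Optional.** Describe the RQ4 AUC as apparent, or correct it with a bootstrap that repeats the model-building steps.

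No extra participants are needed.
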